5.8.1 Discontinuation of Study Therapy after CR

As this is a maintenance trial following complete resection of the primary tumor, it is anticipated that all subjects will continue on therapy for the duration of the post-operative period (52 weeks) even in the absence of disease and even in the event of pathological CR at the time of surgery.

5.9 Subject Replacement Strategy

A subject who discontinues from the trial will not be replaced unless the subject discontinued prior to receiving any doses of study medication.

5.10 Clinical Criteria for Early Trial Termination

Early trial termination will be the result of the criteria specified below:

1. Quality or quantity of data recording is inaccurate or incomplete
2. Poor adherence to protocol and regulatory requirements
3. Incidence or severity of adverse drug reaction in this or other studies indicates a potential health hazard to subjects
4. Plans to modify or discontinue the development of the study drug

In the event of Merck decision to no longer supply study drug, ample notification will be provided so that appropriate adjustments to subject treatment can be made.

5.11 Inclusion of Women and Minorities

Both men and women of all races and ethnic groups are eligible for this trial.

Accrual Targets			
Ethnic Category	Sex/Gender		
	Females	Males	Total
Hispanic or Latino	4	+5	=9
Not Hispanic or Latino	13	+16	=29
Ethnic Category: Total of all subjects	(17)	+(21)	=(38)
Racial Category			
American Indian or Alaskan Native	0	+0	=0
Asian	3	+3	=6
Black or African American	2	+4	=6
Native Hawaiian or other Pacific Islander	0	+0	=0
White	12	+14	=26

Racial Category: Total of all subjects	(17)	+(21)	= (38)
---	------	-------	--------

6.0 TRIAL FLOW CHART

Table 6 Study Flow Chart

Trial Period:	Screening Phase	Treatment Cycles ^a (3 weeks per cycle)									Maintenance Period	End of Treatment and Post-Treatment		
		1	2	3	4	Surgical Period	5	6	7	8+ (to maximum 17 cycles post-op)		End of Treatment (last dose) or Dis-continuation	Safety Follow-up (30 days from last dose)	Survival Follow-Up (phone)
Treatment Cycle/Title:	Main Study Screening Visit 1	1	2	3	4		5	6	7	8+ (to maximum 17 cycles post-op)				
Scheduling Window (Days):	-28 to -1		± 3	± 3	± 3		± 3	± 3	± 3	± 3		± 7	Every 12 weeks	
Administrative Procedures														
Informed Consent	X													
Informed Consent for FBR ^b	X													
Inclusion/Exclusion Criteria	X													
Demographics and Medical History	X													
Prior and Concomitant Medication Review	X	X	X	X	X		X	X	X	X	X	X		
Clinical Procedures/Assessments														
Review Adverse Events	X	X	X	X	X		X	X	X	X	X	X		
12- Lead ECG	X													
2-D Echo	X													
Full Physical Examination	X						X				X			
Directed Physical Examination		X	X	X	X		X	X	X	X		X		
Ht (V1 only), Wt & Vital Signs (T/P/BP/RR)	X	X	X	X	X		X	X	X	X	X	X		
ECOG Performance Status	X		X	X	X		X	X	X	X	X			
Trial Treatment Administration		X	X	X	X		X	X	X	X				
IV Chemotherapy Administration ^c		X	X	X			X	X	X					
Post-study anticancer therapy status											X	Q12 wks		
Survival Status												Q12 wks		
Laboratory Procedures/Assessments: analysis performed by LOCAL laboratory														

Trial Period:	Screening Phase	Treatment Cycles ^a (3 weeks per cycle)									Maintenance Period	End of Treatment and Post-Treatment		
		1	2	3	4	Surgical Period	5	6	7	8+ (to maximum 17 cycles post-op)		End of Treatment (last dose) or Dis-continuation	Safety Follow-up (30 days from last dose)	Survival Follow-Up (phone)
Treatment Cycle/Title:	Main Study Screening Visit 1	1	2	3	4		5	6	7	8+ (to maximum 17 cycles post-op)				
Scheduling Window (Days):	-28 to -1		± 3	± 3	± 3		± 3	± 3	± 3	± 3		± 7	Every 12 weeks	
Pregnancy Test – Urine or Serum β-HCG ^d	X													
PT/INR and aPTT	X													
CBC with Differential	X	X ^e	X	X	X		X	X	X	X	X	X		
Comprehensive Serum Chemistry Panel	X	X ^e	X	X	X		X	X	X	X	X	X		
Urinalysis	X													
T3, FT4 and TSH	X		X		X		X		X	X ^f	X	X		
Efficacy Measurements														
Tumor Imaging	X				X ^g		X ^h		X ⁱ					
Tumor Biopsies/Archival Tissue Collection/Correlative Studies Blood														
Archival or Newly Obtained Tissue Collection	X					X ^j								X ^k
Correlative Studies Blood Collection	X				X						X			

Trial Period:	Screening Phase	Treatment Cycles ^a (3 weeks per cycle)									Maintenance Period	End of Treatment and Post-Treatment		
Treatment Cycle/Title:	Main Study Screening Visit 1	1	2	3	4	Surgical Period	5	6	7	8+ (to maximum 17 cycles post-op)	End of Treatment (last dose) or Dis-continuation	Safety Follow-up (30 days from last dose)	Survival Follow-Up (phone)	
Scheduling Window (Days):	-28 to -1		± 3	± 3	± 3		± 3	± 3	± 3	± 3		± 7	Every 12 weeks	

a. Unless otherwise specified, assessments/procedures are to be performed prior to dose administration on Day 1 of each cycle.
b. Informed consent for the optional Future Biomedical Research (FBR) samples must be obtained before DNA sample is collected.
c. Refer to Section 5.2.2 regarding window for timing of dose administrations.
d. For women of reproductive potential, a negative pregnancy test should be performed within 72 hours prior to first dose of trial treatment.
e. Laboratory screening tests should be repeated prior to cycle 1 day 1 if the screening labs were performed more than 14 days prior to study treatment.
f. Labs will be collected every other cycle during the maintenance period.
g. First imaging assessment will be performed between at week 11 (+/- 14 days) from study initiation.
h. Second imaging assessment will be performed post-operatively prior to resumption of therapy.
i. Subsequent imaging will be performed every 12 weeks (+/- 7 days) from the timing of the initial post-op imaging test (second imaging assessment).
j. Surgical specimens will be evaluated for pathological response for primary end point analysis.
k. There will be an optional tumor biopsy at the time of disease recurrence.

7.0 TRIAL PROCEDURES

7.1 CUMC Research Participant Registration

Confirm eligibility as defined in the section entitled Criteria for Subject Eligibility.

Obtain informed consent, by following procedures defined in section 7.2.1.1.1, General Informed Consent, along with applicable institutional policies and federal regulations.

Only Investigators/Research personnel properly trained and delegated to consent subjects for this protocol will participate in the consenting process. Furthermore, properly delegated/trained Physician Investigators (e.g., MD, MD PhD) are required to sign/verify a protocol specific Eligibility Checklist for each subject enrolled on the study, in addition to providing the relevant source documentation confirmation subject eligibility.

All participants must be centrally registered through the Central Registration Office within Herbert Irving Comprehensive Cancer Center at CUMC prior to initiation of study treatment.

Registration hours are available Monday through Friday from 9:00am – 5:00pm EST (excluding holidays and weekends). Same day patient registrations (and after hour registrations) will be accommodated on a case by case basis provided that the study team has expressed all time sensitive registration concerns/cases in a timely manner to the Central Registration Office.

7.1.1 CPDM Central Registration Procedures:

Within 48 hours of obtaining consent (excluding holidays and weekends), a completed/signed IRB approved informed consent HIPAA form, and demographics forms must be submitted to the CPDM Central Registration Office via an email to [contact] or fax to [contact], with the subject line “AAQ9871 Pending Subject Registration Request (PHI)”. Upon receipt, applicable subject information as well as a “pending eligibility” status will be entered into HICCC’s institutional database. This status will remain until further source documentation is made available to confirm overall patient eligibility. Required materials for all pending registration submissions are as follows:

- Completed/signed IRB approved/stamped Informed Consent Forms, including additional study ICFs (e.g., tissue, DNA, etc.), as applicable.
- The completed/signed IRB approved HIPAA Authorization form
- Completed/signed CPDM ICF checklist
- Completed/signed HICCC personal census form
- Completed/signed CPDM Demographics Note to File

In order to confirm eligibility status, Investigators/designees (e.g., study specific Clinical Research Coordinator/Research Nurse, etc.) must submit the following documentation to the Central Registration Office via email or fax:

- The completed/signed study specific Eligibility Checklist (signed by an Physician level Investigator)
- Copies of source documentation necessary for each item to be verified on the CPDM specific Eligibility Checklist, including but not limited to:
 - Copy of required laboratory test and procedure reports (e.g., hematology, serum chemistry, pregnancy test when applicable, MRI reports, CT/bone scans, etc.)
 - Copy of pathology and surgical reports
 - Copy of clinic note(s) or other appropriate medical records capturing the consent process information, along with providing source documentation of any other items needed for screening/eligibility that are not captured in other source document forms (e.g., positive investigator statements of unique eligibility items not captured via other direct source documentation, concomitant medication lists, etc.)
 - Protocol deviation/waiver approvals (if applicable)
- **Please note:** subject line of email or fax should include the protocol number followed by: “Complete Subject Registration Request (PHI)”.

Upon receipt of the above mentioned documentation, participant eligibility information will be verified by a qualified Central Registration Registrar. If any questions arise during the review process, queries in the form of emails will be addressed to the applicable study team personnel for clarification prior to enrollment. All applicable finalized registration/eligibility information will then be entered into HICCC’s institutional CTMS database by the Central Registration Registrar. Upon completion, an official subject registration notification email will be sent to the PI/research team which will include eligibility/enrollment status, as well as subject ID information. Protocol therapy may not be initiated prior to receipt of this notification from the Central Registration Office.

All screen fail/ineligible subjects, as well as subject’s who withdraw consent prior to enrollment/initiation of protocol therapy must be submitted to the Central Registration office in a manner analogous to the procedures noted above. Applicable source documentation will be required within the corresponding submissions.

7.2 Trial Procedures

The Trial Flow Chart - Section 6.0 summarizes the trial procedures to be performed at each visit. Individual trial procedures are described in detail below. It may be necessary to perform these procedures at unscheduled time points if deemed clinically necessary by the investigator.

Furthermore, additional evaluations/testing may be deemed necessary by the Sponsor-Investigator for reasons related to subject safety. In some cases, such evaluation/testing may be potentially sensitive in nature (e.g., HIV, Hepatitis C, etc.), and thus local regulations may require that additional informed consent be obtained from the subject. In these cases, such evaluations/testing will be performed in accordance with those regulations.

7.2.1 Administrative Procedures

7.2.1.1 Informed Consent

The Investigator must obtain documented consent from each potential subject or each subject's legally acceptable representative prior to participating in a clinical trial.

7.2.1.1.1 General Informed Consent

Consent must be documented by the subject's dated signature or by the subject's legally acceptable representative's dated signature on a consent form along with the dated signature of the person conducting the consent discussion.

A copy of the signed and dated consent form should be given to the subject before participation in the trial.

The initial informed consent form, any subsequent revised written informed consent form and any written information provided to the subject must receive the IRB/ERC's approval/favorable opinion in advance of use. The subject or his/her legally acceptable representative should be informed in a timely manner if new information becomes available that may be relevant to the subject's willingness to continue participation in the trial. The communication of this information will be provided and documented via a revised consent form or addendum to the original consent form that captures the subject's dated signature or by the subject's legally acceptable representative's dated signature.

Specifics about a trial and the trial population will be added to the consent form template at the protocol level.

The informed consent will adhere to IRB/ERC requirements, applicable state laws and federal regulations.

7.2.1.2 Inclusion/Exclusion Criteria

All inclusion and exclusion criteria will be reviewed by the investigator or qualified designee to ensure that the subject qualifies for the trial.

7.2.1.3 Medical History

A medical history will be obtained by the investigator or qualified designee. Medical history will include all active conditions, and any condition diagnosed within the prior 10 years that are considered to be clinically significant by the Investigator. Details regarding the disease for which the subject has enrolled in this study will be recorded separately and not listed as medical history.

7.2.1.4 Prior and Concomitant Medications Review

7.2.1.4.1 Prior Medications

The investigator or qualified designee will review prior medication use, including any protocol-specified washout requirement, and record prior medication taken by the subject within 28 days before starting the trial. Treatment for the disease for which the subject has enrolled in this study will be recorded separately and not listed as a prior medication.

7.2.1.4.2 Concomitant Medications

The investigator or qualified designee will record medication, if any, taken by the subject during the trial. All medications related to reportable SAEs and ECIs should be recorded as defined in Section 7.2.1.4.2.

7.2.1.5 Disease Details and Treatments

7.2.1.5.1 Disease Details

The investigator or qualified designee will obtain prior and current details regarding disease status.

7.2.1.5.2 Prior Treatment Details

The investigator or qualified designee will review all prior cancer treatments including systemic treatments, radiation and surgeries.

7.2.1.5.3 Subsequent Anti-Cancer Therapy Status

The investigator or qualified designee will review all new anti-neoplastic therapy initiated after the last dose of trial treatment. If a subject initiates a new anti-cancer therapy within 30 days after the last dose of trial treatment, the 30 day Safety Follow-up visit must occur before the first dose of the new therapy. Once new anti-cancer therapy has been initiated the subject will move into survival follow-up.

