2.0 TRIAL DESIGN

2.1 Trial Design

This is a non-randomized, multi-site, open-label trial of pembrolizumab and chemotherapy in subjects with gastric or gastroesophageal junction adenocarcinoma. Up to 38 subjects may be enrolled in a single cohort, for a sample of 28 evaluable subjects, to assess the efficacy of combination therapy with standard peri-operative chemotherapy in resectable gastric or GE junction adenocarcinoma. The trial was initiated at 2 sites and two additional sites were subsequently added to increase enrollment.

All study subjects will receive standard of care chemotherapy for 3 cycles prior to and 3 cycles following surgery in combination with Pembrolizumab with an additional cycle of Pembrolizumab (4 total) in the pre-operative period. Additionally, subjects will complete 12 months of maintenance Pembrolizumab (14 additional doses to complete 17 post-operative cycles) following completion of post-operative chemotherapy. The primary efficacy endpoint will be **pathologic complete response (pCR) rate** among all enrolled subjects. Recurrence or disease progression will be determined based on RECIST 1.1 and investigator assessment.

Adverse events will be monitored throughout the trial and graded in severity according to the guidelines outlined in the NCI Common Terminology Criteria for Adverse Events (CTCAE) version 4.0.(As referenced in Appendix 13.2)

After the end of treatment, each subject will be followed for 30 days for adverse event monitoring. Serious adverse events and Events of Clinical Interest (ECI) will be collected for 90 days after the end of treatment or 30 days after the end of treatment if the subject initiates new anticancer therapy, whichever is earlier. Subjects who discontinue treatment for reasons other than disease recurrence will have post-treatment follow-up for disease status until disease recurrence, withdrawing consent, or becoming lost to follow-up. All subjects will be contacted by telephone for overall survival until death, withdrawal of consent or the end of the study, whichever comes first.

[figure not shown]

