5.8 Subject Withdrawal/Discontinuation Criteria

Subjects may withdraw consent at any time for any reason or be dropped from the trial at the discretion of the investigator should any untoward effect occur. In addition, a subject may be withdrawn by the investigator or the Sponsor-Investigator if enrollment into the trial is inappropriate, the trial plan is violated, or for administrative and/or other safety reasons. Specific details regarding discontinuation or withdrawal are provided in Section 7.1.4 – Other Procedures.

Even if a subject discontinues trial treatments, they will be encouraged to continue to participate in collection of data regarding the endpoints, including DFS and OS.

A subject must be discontinued from the trial treatments for any of the following reasons:

- The subject or legal representative (such as a parent or legal guardian) withdraws consent.
- Confirmed radiographic disease progression or recurrence
- Unacceptable adverse experiences as described in Section 5.2.1.2
- Intercurrent illness that prevents further administration of treatment
- Investigator's decision to withdraw the subject
- The subject has a confirmed positive serum pregnancy test
- Noncompliance with trial treatment or procedure requirements
- The subject is lost to follow-up
- Completed 12 months of uninterrupted treatment with pembrolizumab following surgical resection or 17 administrations of study medication, whichever is later.

Note: 12 months of study medication is calculated from the date of first dose following surgical resection.

- Administrative reasons

The End of Treatment and Follow-up visit procedures are listed in Section 6.0 (TRIAL FLOW CHART) and Section 7.1.5 (Visit Requirements). After the end of treatment, each subject will be followed for 30 days for adverse event monitoring (serious adverse events will be collected for 90 days after the end of treatment as described in Section 7.2.3.1). Subjects who discontinue for reasons other than progressive disease will have post-treatment follow-up for disease status until disease progression or recurrence, withdrawing consent or becoming lost to follow-up. After documented disease progression each subject will be followed by telephone for overall survival until death, withdrawal of consent, or the end of the study, whichever occurs first.

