7.2.5.3.2 Survival Follow-up

Once a subject experiences confirmed disease progression or completes 17 cycles of post-operative therapy, the subject moves into the survival follow-up phase and should be contacted by telephone every 12 weeks to assess for survival status until death, withdrawal of consent, or the end of the study, whichever occurs first.

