8.1.2 Secondary Endpoint

The secondary endpoints are ORR, DFS and OS. DFS is defined as time from Cycle 1 Day 1 treatment administration to the first documented event of: disease progression, disease recurrence following surgery (preferably biopsy proven), or death- whichever occurs first. Overall Survival (OS): time from Cycle 1 Day 1 treatment administration to death due to any cause.

The secondary hypothesis of this study is that combination therapy with immune checkpoint blockade and chemotherapy used in the perioperative period will eradicate micrometastatic disease and improve disease free survival (DFS).

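### Section 7.2.1.5.3 ends disease follow-up when new anti-cancer therapy starts, contrary to Sections 2.1 and 5.8, and the SAP does not say how DFS handles such subjects

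*Combined protocol and SAP*

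**What the plan says.** Two rules cover a subject who has stopped trial treatment without a documented DFS event.

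- **Rule A, Section 7.2.1.5.3:** "Once new anti-cancer therapy has been initiated the subject will move into survival follow-up". The trigger is the new therapy alone. Section 7.2.5.3.2 describes the content of that phase: subjects "should be contacted by telephone every 12 weeks to assess for survival status until death", consent withdrawal or study end. In the flow chart (Section 6.0), as far as the extracted table can be read, the survival column has no scheduled tumor imaging.
- **Rule B, Sections 2.1 and 5.8:** under Section 2.1, subjects who stop for reasons other than recurrence "will have post-treatment follow-up for disease status until disease recurrence, withdrawing consent, or becoming lost to follow-up". Section 5.8 likewise requires "post-treatment follow-up for disease status until disease progression or recurrence, withdrawing consent or becoming lost to follow-up". It places the telephone phase later: "After documented disease progression each subject will be followed by telephone for overall survival until death".

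Section 8.1.2 starts the DFS clock at first dose ("DFS is defined as time from Cycle 1 Day 1 treatment administration") and counts progression, recurrence after surgery or death as events. New therapy is not an event. Section 8.2.1 names Kaplan-Meier and a 24-month DFS estimate with a 95% interval, and gives no censoring rule. Section 8.2.5.1 includes every subject who received one dose. The synopsis (Section 1.1) calls DFS a key secondary outcome, and Section 8.1.3 uses 24-month DFS as one way to define good response in the biomarker comparison.

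**The concern.** A site cannot follow both rules for a subject who starts other therapy before a documented event. Under Rule A the trial stops looking for progression and recurrence, which are two of the three DFS event types. Assessments missed for that reason are hard to recover later.

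The protocol opens several routes to this situation. Section 8.2.5.1 foresees stopping before surgery for toxicity or physician discretion. Section 5.5.2 says subjects who need a prohibited treatment should be removed from the trial. Section 8.2.5.3.1 generally dates recurrence at a positive biopsy, so treatment for suspected recurrence could begin before an event is on record.

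Because the SAP is silent, one analyst could censor at the switch, while another could carry the subject forward and count only a later death. Both would comply with the plan, and they could report different 24-month DFS estimates from the same data.

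**Working it through.** **1. The passages side by side.** The plan states no DFS rate, event count or power, so there is no DFS figure to reproduce. The first check is textual: is starting new therapy a reason to end disease assessment or to enter telephone follow-up?

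| Section | Is new therapy a trigger? |
|---|---|
| 7.2.1.5.3 | Yes, on its own |
| 2.1 | No: recurrence, consent withdrawal, loss to follow-up |
| 5.8 | No: the same list, with progression added |
| 7.2.2.7.2 (end of imaging) | No: but completion of study treatment is listed |
| 7.2.5.3.2 (entry to telephone phase) | No: "Once a subject experiences confirmed disease progression or completes 17 cycles of post-operative therapy" |

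Section 5.5.2 prohibits no therapy in the post-treatment follow-up phase, so that phase can include subjects on new therapy. Section 7.2.1.5.3 is the outlier.

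**2. Possible size if subjects are censored at the switch.** All inputs except the 38 subjects and the 24-month landmark are assumed: exponential DFS with a 30-month median, k = 2, 4 or 6 subjects event-free and switched at month 4, and hazard after the switch multiplied by m.

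- Monthly hazard: h = ln 2 / 30 = 0.0231.
- Chance of staying event-free from month 4 to 24 without a switch: exp(−20h) = 0.630.
- The same after a switch: exp(−20hm) = 0.397 at m = 2 and 0.157 at m = 4.
- Kaplan-Meier gives censored subjects the 0.630. Overstatement = (k/38) × [0.630 − exp(−20hm)].

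| m | k = 2 | k = 4 | k = 6 |
|---|---|---|---|
| 1 | 0 | 0 | 0 |
| 2 | 1.2 | 2.5 | 3.7 |
| 4 | 2.5 | 5.0 | 7.5 |

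(percentage points)

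If k instead counts subjects marked at baseline, who switch only if event-free at month 4, each entry is multiplied by exp(−4h) = 0.912. The m = 2 row becomes 1.1, 2.2 and 3.4, and the m = 4 row 2.3, 4.5 and 6.8. Overall this is about 1 to 7 points.

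**3. Possible size if only deaths are captured.** Assume in addition that death follows recurrence by 6 months. A switched subject then counts as event-free at month 24 unless recurrence came by month 18, which is 14 months after the switch. Overstatement = (k/38) × [exp(−14hm) − exp(−20hm)].

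- m = 1: 0.724 − 0.630 = 0.094, giving 0.5, 1.0 and 1.5 points for k = 2, 4 and 6.
- m = 2: 0.524 − 0.397 = 0.127, giving 0.7, 1.3 and 2.0 points.
- m = 4: 0.274 − 0.157 = 0.117, giving 0.6, 1.2 and 1.8 points.

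This bias does not vanish at equal risk, because it comes from late dating.

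**4. Against sampling error.** At these inputs 24-month DFS is exp(−24h) = 0.574. With 38 subjects and no censoring, the standard error is √(0.574 × 0.426 / 38) = 0.080, so the 95% half-width is about 16 points.

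**5. A second route out of disease assessment.** Section 7.2.2.7.2 ends imaging at completion of study treatment, and Section 7.2.5.3.2 moves subjects who finish 17 post-operative cycles to the telephone. Section 1.0 puts average treatment at 16 months, which is 24 − 16 = 8 months short of the landmark. Section 5.8 counts completion among the reasons for stopping treatment, so its promise of disease-status follow-up covers these subjects too.

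**The case against.** The strongest reply is that the conflict is one of wording and that no bias has been shown. Much of this stands.

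- A reader might infer that switched subjects are censored. No passage says so. Deaths are still collected by telephone and are DFS events, and Section 5.8 encourages subjects who stop treatment to keep contributing DFS and OS data.
- A reader might infer that switched subjects are poor-risk, so that DFS is certainly overstated. The documents give neither their reasons for switching nor their prognosis. At equal risk, censoring causes about no bias.
- A reader might link the problem to the 10 of 38 subjects (38 − 28) not expected to be evaluable at surgery. Section 1.1 does not connect that number to switching. Some of the ten will have stopped for progression, which is already a DFS event, and imaging around week 11 is there to assess response and eligibility for surgery.
- A reader might take the survival phase to contain no disease information at all. What is absent is scheduled imaging. Therapy status appears to be recorded every 12 weeks, and an optional biopsy at recurrence appears in the same part of the flow chart, although the extracted table may be broken.

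Every overstatement computed here is also below one standard error of 24-month DFS, and DFS carries no test or decision rule. None of this removes the contradiction. The silence on censoring is itself the gap, and capturing deaths alone still dates events late.

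**Conclusion.** The contradiction is real: for a subject who starts new therapy before a documented DFS event, Section 7.2.1.5.3 ends what Sections 2.1 and 5.8 continue. The SAP does not settle how that subject enters the DFS analysis. Subjects who switch after a documented event are unaffected, as is the primary pCR test.

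The direction and size of any bias are conditional. Censoring at the switch may overstate 24-month DFS by about 1 to 7 points, but only under an assumed 30-month median, 2 to 6 of 38 switched at month 4, and a doubled to four-fold hazard. Capturing deaths only may overstate it by about 0.5 to 2 points under the same inputs and an assumed 6-month lag to death, including at equal risk. The documents do not support a firm statement that DFS is overstated. The point deserves action because it affects a key secondary endpoint and is inexpensive to correct.

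**What to change.** 1. Reconcile Section 7.2.1.5.3 with Sections 2.1 and 5.8 so that starting new therapy does not by itself end disease-status follow-up for DFS. Routine-care scan results can be used until progression, recurrence or death.
2. In the same edit, reconcile Sections 7.2.2.7.2 and 7.2.5.3.2 with Section 5.8, so that disease status is collected through the 24-month landmark in subjects who complete treatment. Changing Section 7.2.1.5.3 alone would leave this second gap open.
3. In Section 8.2.1, state that the main DFS analysis does not censor at new anti-cancer therapy. A sensitivity analysis counting new therapy as an event is a reasonable option.

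The change alters no trial treatment. It costs wording and a small amount of extra data collection in subjects who have left treatment.
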